#### Breakdown of Aims 1-3

- Aim 1: 10 moderate drinkers
- Aim 2: 10 moderate drinkers

- Aim 3: 30 moderate drinkers (minus drinkers from chosen tracer in Aim 1 or 2), and 30 AUD

#### **4.2 Subject Selection:**

Moderate drinker participating patients will self-report drinking consistent with at least one binge alcohol event in the past three months but not meet DSM-5 criteria for AUD to ensure that accustomed drinking levels are not exceeded in the laboratory. AUD subjects will meet DSM-5 criteria for current Alcohol Use Disorder. Subjects will be recruited mainly from New Haven County, although enrollment is not limited to this region. All research subjects will be recruited under guidelines of the Yale University Institutional Review Board (Human Investigation Committee). Subjects will be recruited from the community at large via IRB-approved advertising (television, newspaper, postings in community locations, Craigslist, Facebook).

#### **Screening Evaluation**

All screening procedures will be performed by a trained research assistant or study coordinator. Initial screening will be performed over the telephone. Potentially eligible subjects will undergo an initial in-person screening evaluation within 2 months of PET scanning, this will be located either at [name], the Yale PET Center, CMHC, or HRU. Current non treatment seeking inpatient subjects at the CNRU will be able to participate if participation in their current study is not a conflict with this study, and vice versa. The purpose of this evaluation is to ensure that subjects meet study criteria. Breath alcohol (BAC) levels will be monitored for subjects before the intake session. After informed consent is obtained, the structured clinical interview for DSM-5 Axis I Disorders (SCID-5) will be used to exclude primary psychiatric and substance use disorders other than alcohol use disorder. A C-SSRS will be performed if suicidality is revealed in the SCID or other questionnaires. A medical history, vital signs, physical examination, and EKG will be performed. The Timeline-Follow Back interview for Alcohol (TLFB) will be used to characterize quantity and frequency of alcohol drinking up to 90 days prior to enrollment. The Lifetime Drinking History, a retrospective interview procedure, will be used to characterize lifetime patterns and quantities of alcohol. Subjects will also indicate the maximum amount of drinks consumed in a single 24-hour period over the last three months. Several laboratory tests will be performed at this visit, which include a complete blood count (CBC), chemistry profile, thyroid function studies, HIV, serum  $\beta$ -HCG (women only), urinalysis, liver function tests, and urine toxicology screen. All female subjects will undergo a pregnancy test at the time of screening. Additionally, urine pregnancy tests will be done on the day of each PET scan before radiotracer injection. Urine drug screens will be done at intake, MRI, and on PET days.

#### **4.3 Assessments:**

All participants will be screened initially using a telephone screen that will include questions to evaluate medical history, personal and familial psychiatric and smoking history. A wide range of measures, such as psychiatric and substance abuse history, medical assessments and affective symptoms will be measured during the intake evaluation.

##### **4.3.a. General Intake Assessments**

1. Structured Clinical Interview for DSM-5 Axis I Disorders The psychotic screening and depression sections of the Structured Clinical Interview for DSM-5 Axis I Disorders (SCID-5) will be used to determine whether subjects meet exclusion criteria for diagnosis of primary psychiatric and substance use disorders other than alcohol use disorder.
2. Illicit Drug/Pregnancy Screen A urine sample may be collected to determine current illicit drug use (for all potential subjects). In addition, serum samples will be collected at the intake visit and urine samples will be collected on each PET scan day to confirm that the subject is not pregnant.

3. Demographic Questionnaire This questionnaire will obtain: (1) basic demographic information including age, gender, marital status, employment status, occupation, (2) alcohol/drug history, (3) family history of alcohol/drug use, depression, anxiety, and smoking history.
4. Medical History This questionnaire will obtain a basic medical history (personal and family) including past or current conditions such as neurological, endocrine, cardiovascular, renal, liver, and thyroid pathology. Current body weight and current medications will also be assessed.
5. Medical Assessments will include a physical exam by a state licensed physician, an EKG, and laboratory tests which may include a complete blood count, blood urea nitrogen, creatinine, fasting blood sugar, electrolytes, liver function tests, thyroid function tests (including T3, T4, T3RU, estimated free T4), thyroid stimulating hormone levels, urine toxicology, and urinalysis. Female subjects will have serum pregnancy tests.
6. Multidimensional Scale of Perceived Social Support (MSPSS) is a brief research tool designed to measure perceptions of support from 3 sources: Family, Friends, and a Significant Other.
7. Barratt Simplified Measure of Social Status (BSMSS) is a measure of socio-economic status.

#### **4.3.b. Mood and Sleep Measures**

We may obtain these measures at intake, up to two times on PET scan days, and the morning following the alcohol session.

1. Center for Epidemiological Studies Depression Scale (CES-D) The CES-D is a 20-item self-report instrument, which has been extensively used in both clinical and nonclinical populations to measure the frequency and severity of depressive symptoms over the past week. The CES-D, which has been used to document the severity of depressive symptoms in adults and has been shown to be a sensitive measure of negative affect in smokers, will be used in the proposed studies to measure levels of mild depressive symptoms.
2. Anxiety: The State-Trait Anxiety Inventory is a 40-item, self-report measure, comprised of two subscales. The State-Anxiety scale is 20 items and assesses transitory states characterized by feelings of tension, apprehension, and heightened autonomic reactivity. The Trait-Anxiety scale is 20 items and assesses stable individual differences in anxiety proneness.
3. Impulsivity: Barratt Impulsiveness Scale (BIS; ) is a 30 item self-report instrument designed to assess the personality/behavioral construct of impulsiveness.
4. Beck Depression Inventory: This widely used 21 item self-report instrument will be used to assess depressive symptomatology in addition to the SCID (43).
5. Sleep Quality: The Pittsburgh Sleep Quality Index (PSQI) is a 19 item self-rated questionnaire that assesses sleep quality and disturbances over the previous month.
6. Post-Traumatic Stress Disorder Checklist (PCL) is a 20-item self-report measure that assesses the DSM symptoms of PTSD. We will use the PCL-5, a 20-item self-report measure that assesses the 20 DSM-5 symptoms of PTSD.
7. Life Events Checklist LEC-5 assesses several possible traumatic events that a subject may have experienced.
8. The CAPS-5 is a 30-item structured interview that can be used to: Make current (past month) diagnosis of PTSD , make lifetime diagnosis of PTSD, and assess PTSD symptoms over the past week.
9. Columbia Suicide Severity Rating Scale (CSSRS) is a clinician administered questionnaire to assess suicidality. In the event of an unexpected outcome, subjects will be referred to the Emergency Department for risk assessment.

#### **4.3.c. Alcohol and other Drug Measures**

We may obtain these measures at intake and also on PET scan days.

1. Timeline Followback for alcohol, tobacco, and illicit drugs. Questionnaire to measure the amount of alcohol, tobacco, and other drugs that have been used in the past 30 days.
2. Lifetime Drinking History is a structured interview designed to provide quantitative indices of alcohol consumption patterns from the onset of regular drinking.
3. Short Inventory of Problems provides a psychometric inventory of adverse consequences from substance use.
4. Drinking Motives Questionnaire characterizes individual motivations for consuming alcohol.
5. Fagerstrom Test for Nicotine Dependence (FTND). This will be used to measure the severity of nicotine dependence. It is a 6-item scale with an internal consistency of .61 and its total score is closely related to biochemical measures of intensity of smoking.
6. Smoking History. This questionnaire will assess basic smoking status and history such as number of years smoked, number and length of quit attempts, reasons for quitting, and second hand smoke exposure.
7. Nicotine Withdrawal Checklist. This measures the severity of eight withdrawal symptoms on 5-point Likert scales.

#### **4.3.d. Cognitive Measures**

We may obtain these measures at intake, up to two times on PET scan days, and the morning following the alcohol session.

1. Cogstate Battery (30 minutes) – This computerized test battery will assess memory and cognition. The tasks may include:
  - a. International Shopping List Task – a computerized task to assess verbal learning and memory.
  - b. Groton Maze Learning Task – a computerized task to assess executive function and spatial problem solving.
  - c. Detection Task – a computerized task to assess psychomotor function and speed of processing.
  - d. Identification Task – a computerized task to assess visual attention and vigilance.
  - e. One Card Learning Task – a computerized task to assess visual learning and memory.
  - f. One Back Task and Two Back Task – computerized tasks to assess attention and working memory.
2. Probabilistic Reward Task (PRT) – The PRT has been successfully used to assess reward responsiveness (51-53). In each trial, subjects choose which of two difficult-to-differentiate stimuli was presented. Stimuli consist of simple cartoon faces (diameter: 25 mm; eyes: 7 mm) presented in the center of the monitor. At the beginning of the trial, the face has no mouth. After a given delay, either a straight mouth of 11.5 mm ("short mouth") or 13 mm ("long mouth") is presented for 100 ms. Subjects are instructed to press an appropriate button to decide whether a long or small mouth had been presented. Unbeknownst to subjects, correct identification of one stimulus ("rich stimulus") is rewarded three times more frequently ("Correct! You won 20 cents") than the other ("lean") stimulus. In healthy controls, this reinforcement schedule leads to a response bias (i.e., a preference for the more frequently rewarded stimulus). The degree of response bias toward the more frequently reinforced alternative will be used for operationalizing sensitivity to reward.
3. Probabilistic Reversal Learning Task (PRLT) – The PRLT has been shown to effectively detect "belief updating" behavior through the use of the Hierarchical Gaussian Filter model. This task uses a 3-option probabilistic reversal-learning paradigm which requires participants to choose between options with unknown, unequal probabilities of reward. Three decks of cards are displayed on a computer monitor for 160 trials. Participants select a deck on each trial by pressing a predesignated key on a keyboard. We advise participants that each deck contains either winning or losing cards (e.g. +100, -50 points, etc.), but in different amounts. We also state that the best deck may change. Participants are instructed to find the best deck and

earn as many points as possible. Probabilities switch between decks when the highest probability deck is selected in 9 out of 10 consecutive trials (performance-dependent reversal). It is predicted that AUD participants may interpret probabilistic errors (e.g., the occasional instance when a good option does not yield reward), as reversal errors (the world has changed) and thus switch their choices prematurely.

#### **4.4 Procedures**

##### **Screening, Evaluation and Clinical Ratings**

Screening, evaluation and clinical ratings (as described above) are obtained during the screening process.

##### **Magnetic Resonance Imaging (up to 1 hour)**

Magnetic resonance imaging (MRI) scans (3T) will be collected in each subject to co-register PET and MRI for image analysis as well as collect resting state data. MRI is without contrast. Within approximately two weeks of the PET studies, an MRI will be acquired at the Yale University MRI Center. Subjects will be taken through a ferromagnetic metal detector before entering the scan room.

3T Scan sequence:

Series 1: 3 plane localize

Series 2: Sag 3d tfl; 256fov; 1mm thick slices; 176 slices total; TE 2.77; TR 2530; TI 1100; FA 7; 256X256 1 average.

Series 3 – Resting state: Ep2d bold; 210fov; 2.5mm thick slices; TE 30; TR 3400; FA 85; 84x84 (Run twice).

MR images provide a matching anatomical atlas for creating individualized region-of-interest templates for each subject. We will also examine functional connectivity at rest.

If an MR image is already on file at the PET Center, and has been collected within a reasonable time period, a new MRI may not need to be collected.

A member of the research staff will accompany the subject and stay for the duration of the MRI.

##### **PET Scans**

PET experiments will be conducted at the Yale University PET Center. Subjects may have up to three [C]ABP688 PET scans, and/or up to three [F]FPEB PET scans for a maximum total of six scans (including possible rescheduled scans, 1 per tracer). Subjects will also be asked to refrain from drinking caffeinated beverages on imaging days, and from drinking alcoholic beverages 48 hours prior to imaging days.

Upon arrival at the PET center, subjects will complete questionnaires on urges, withdrawal symptoms, and mood. Plasma will be drawn before scans to measure drug levels in the blood. Urine drug tests will be performed before all PET scans. To ensure overnight abstinence for individuals with alcohol use disorder, subjects will be invited to stay inpatient at the CNRU the night before their PET scans unless there are scheduling conflicts with the subject. Confirmation of alcohol abstinence over the previous 48 hours will be made via self-report and BAC measures, and session will be rescheduled if positive.

*For all women, a urine pregnancy test will be performed at the beginning of the imaging day, prior to radiotracer injection, at the Yale University PET Center.*

For all aims, up to three total [F]FPEB PET scans may be acquired per subject. Imaging data will be acquired using bolus or bolus plus constant infusion of  $\leq 20$  mCi [F]FPEB. After baseline mGlu5 availability is measured, subjects will participate in i.v. alcohol infusion (targeting 60 mg/dL). This dose was selected to achieve mild to moderate levels of intoxication, consistent with the aims of the proposal. [F]FPEB PET scanning will begin as soon as possible (i.e., not more than 30 min after the subject completes the alcohol challenge) to capture the peak glutamate response. This timing is consistent with previous reports studying dopamine release in response to alcohol challenge. Blood samples will be collected throughout all [F]FPEB PET scans and during the alcohol administration.

For aims 1 and 2. up to three total [C]ABP688 PET scans may be acquired per subject. Imaging data will be acquired using bolus or bolus plus constant infusion of  $\leq 20$  mCi [C]ABP688. After baseline mGlu5 availability is measured, subjects will participate in i.v. alcohol administration (targeting 60 mg/dL ). [C]ABP688 PET scanning will begin as soon as possible (i.e., not more than 30 min after the subject completes the alcohol challenge) to capture the peak glutamate response. This timing is consistent with previous reports studying dopamine release in response to alcohol challenge. Blood samples will be collected throughout all [C]ABP688 PET scans and during the alcohol administration.

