The site will be anesthetized with lidocaine prior to arterial line insertion. The arterial line may remain in place for the whole day of scanning, after which it will be removed by trained nursing staff at the Yale PET Center. PET data are acquired while subjects rest with an HRRT PET scanner (207 slices, resolution better than 3 mm FWHM). A transmission scan will be obtained for each emission scan. Motion correction may be performed dynamically with measurements from the Vicra (NDI Systems, Waterloo, Ontario) used by a dedicated list-mode reconstruction algorithm. Acquisition of list-mode emission data will begin shortly before IV administration of up to 20 mCi of high-specific activity [C]ABP688 or up to 5 mCi of high-specific activity [F]FPEB and will continue for up to 120 minutes post-injection for [C]ABP688 or up to 180 minutes post-injection for [F]FPEB. Dynamic images of radioactivity concentration will be reconstructed with corrections for measured attenuation, normalization, random events, scatter, and deadtime. Subjects will be asked to void after the scan is completed to reduce radiation exposure to the bladder. Venous blood samples to measure plasma blood alcohol concentration (BAL) and peripheral cytokine levels will also be acquired. After the completion of the days final PET scan, the IVs will be removed. Monitoring of vitals will continue for at least 30 minutes before subject returns to the CNRU or HRU.

List mode data will be reconstructed with MOLAR^43, with corrections for attenuation, normalization, and motion to create high resolution images. Early PET image data will be registered to the subjects T1-weighted

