#### **Risks Associated with Radiation**

The Yale University Radioactive Drug Research Committee (YU RDRC) will review the use of radiation in this research study, and no subjects will be scanned until approval is obtained. This research study involves exposure to radiation from [C]ABP688 and/or [F]FPEB . This radiation exposure is not necessary for medical care and is for research purposes only.

The maximum amount of radiation an individual subject may receive in this study would be if they participated in both Aim 1 and Aim 2 of this study. This participation would involve two injections of  $\leq 20$  mCi of [C]ABP688 (0.2360 rem each), two injections of  $\leq 5$  mCi of [F]FPEB (0.312 rem each), plus a small amount of radiation from the transmission scans of the brain.

Although each organ will receive a different dose, the maximum amount of radiation exposure subjects could receive from this study is equal to an effective dose of **1.102 rem** for a total of up to 40 mCi of [C]ABP688 and 10 mCi [F]FPEB from four total injections and 4 transmission scans (.0014rem each). This calculated value is used to relate the dose received by each organ to a single value. Subjects may get an additional injection of either radiotracer if needed due to scan failure after injection, this would bring the total possible rem to **1.652 Rem** from 3 injections of each tracer and 6 transmission scans.

Subjects may participate in more than one aim, not to exceed **1.652 Rem** total and not to exceed 3 injections of either tracer total.

The amount of radiation subjects will receive in this study is below the dose guidelines established by the FDA and monitored by **the Yale University Radioactive Research Committee** for research subjects. This guideline sets an effective dose limit of 5 rem per year.

Adverse effects of the radiopharmaceuticals in this study have not been reported. However, the possibility exists for a rare reaction to any of the substances or procedures to which a subject is exposed.

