#### [F]FPEB

The radiotracer [F]FPEB has previously been used in human subjects, including Yale University. Over 200 individuals and over 352 injections have been imaged at Yale University. No subjects have reported any adverse event with this radiotracer. However, subjects will be monitored carefully during and after the PET scan for any potential side effects.

[F]FPEB is administered intravenously at doses up to 5 mCi per single administration which is below the 21 CFR 361.1 estimated permissible single administration dose limit of 7 mCi based on dosimetry calculations with 3.5 h voiding period.

4. **Source:** Identify the source of the radiotracer to be used.

[C]ABP688 and [F]FPEB will be synthesized at the Yale University PET Center radiochemistry Laboratory under the supervision of [name] and [name].

5. **Storage, Preparation and Use:** Describe the method of storage, preparation, stability information, method of sterilization and method of testing sterility and pyrogenicity.

[C]ABP688 and [F]FPEB will be prepared at the Yale PET Center in accordance with procedures and quality specifications described in local Drug Master File (DMF) approved by the Yale University Radioactive Drug Research Committee (YURDRC) and the Yale University Radiation Safety Committee (YURSC).

Due to the short half-life, PET drugs are produced *ex tempore* and formulated immediately before administration, and therefore there are no issues with storage or stability. PET drug products are stored at room temperature and are stable for at least 60 minutes after preparation.

The preparation of sterile and pyrogen free PET drug products is validated prior to human use. Sterility is achieved by passing the PET drug products through a 0.22 micron membrane filter during the last step of the formulation process. Due to the short half-life, a sample of the PET drug product is tested for sterility *ex post facto* for further confirmation. However and prior to release for administration, a bubble point test is performed on the membrane filter used for terminal sterilization in order to validate and verify its integrity during the filtration process. Also prior to release of the final PET drug product for administration, the level of endotoxin in each batch is determined quantitatively using the FDA approved Charles River Laboratory's Portable Testing System (Endosafe®-PTS).

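### The PET Scans procedure allows up to 20 mCi of [18F]FPEB per scan, against 5 mCi everywhere else in the protocol and a quoted single-administration limit of 7 mCi

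*Combined protocol and SAP*

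**What the plan says.** The PET Scans text in Section 4.4 covers [18F]FPEB for all aims: "Imaging data will be acquired using bolus or bolus plus constant infusion of $\leq 20$ mCi [ 18 F]FPEB". The paragraph on the other tracer has the same form: "Imaging data will be acquired using bolus or bolus plus constant infusion of $\leq 20$ mCi [ 11 C]ABP688".

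The protocol gives a different [18F]FPEB activity in three places:

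- **PET Data Acquisition and Analysis** has the injection as "up to 5 mCi of high-specific activity [ 18 F]FPEB".
- **Section 10, Risks Associated with Radiation**, pairs at most 5 mCi of [18F]FPEB with 0.312 rem per injection. For the case of two scans with each tracer it gives a total of up to "40 mCi of [ 11 C]ABP688 and 10 mCi [ 18 F]FPEB from four total injections".
- **Section II.A, [18F]FPEB**, says that the tracer "is administered intravenously at doses up to 5 mCi per single administration" and that this is below the "estimated permissible single administration dose limit of 7 mCi based on dosimetry calculations". That limit is stated for a 3.5 h voiding period.

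For [11C]ABP688 the ceiling is 20 mCi throughout, and its quoted single-administration limit is 82 mCi.

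**The concern.** One protocol cannot set both 20 mCi and 5 mCi as the maximum for the same injection. The larger figure stands in the procedure text that applies to every [18F]FPEB scan, and no reason is given for a higher activity when a constant infusion is added to the bolus.

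What is at stake is participant safety. Someone working from the PET Scans text alone would find written permission for an injection well above a regulatory limit that the same document quotes. If [18F]FPEB is chosen for Aim 3, the text governs scans in 30 moderate drinkers and 30 people with alcohol use disorder.

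Eligibility is also touched. Exclusion criterion 12 and Section 11 rule out people whose annual research exposure, with this study included, would exceed 5 rem. How much prior exposure is acceptable depends on how much this study adds.

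**Working it through.** **Inputs** (Risks Associated with Radiation, unless noted)

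- [11C]ABP688: at most 20 mCi, 0.2360 rem per injection
- [18F]FPEB: at most 5 mCi, 0.312 rem per injection
- Transmission scan: 0.0014 rem each, one per PET scan
- Stated maxima: 1.102 rem (two injections of each tracer) and 1.652 rem (three of each). The second is an express cap.
- Annual guideline: 5 rem
- [18F]FPEB single-administration limit: 7 mCi (Section II.A)
- [18F]FPEB ceiling in PET Scans: 20 mCi

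**Step 1. Reproduce the stated totals.**

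- Two of each: 2 × 0.2360 + 2 × 0.312 + 4 × 0.0014 = 1.1016 rem (stated 1.102)
- Three of each: 3 × 0.2360 + 3 × 0.312 + 6 × 0.0014 = 1.6524 rem (stated 1.652)

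Both agree. These sums use rem per injection, so they do not by themselves identify the activity. The link to 5 mCi is that the radiation section attaches 0.312 rem to injections of at most 5 mCi.

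**Step 2. Compare activities, with no dosimetry assumption.**

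- Against the 5 mCi ceiling: 20 / 5 = 4.0
- Against the 7 mCi limit: 20 / 7 = 2.86
- Against the 10 mCi total for two planned injections: 20 / 10 = 2.0
- Against three injections at 5 mCi, the most any subject may have: 3 × 5 = 15 mCi, still less than 20

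**Step 3. Convert to rem, assuming effective dose is proportional to activity.** The documents give no dose for 20 mCi, so this is an assumption.

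- Dose per mCi: 0.312 / 5 = 0.0624 rem
- One injection of 20 mCi: 20 × 0.0624 = 1.248 rem

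| Scans, with [18F]FPEB at 20 mCi | Calculation | rem |
|---|---|---|
| One [18F]FPEB | 1.248 + 0.0014 | 1.249 |
| Two [18F]FPEB | 2 × 1.2494 | 2.499 |
| Two of each tracer | 2 × 0.2360 + 2 × 1.248 + 4 × 0.0014 | 2.974 |
| Three of each tracer | 3 × 0.2360 + 3 × 1.248 + 6 × 0.0014 | 4.460 |

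One scan stays under the 1.652 rem cap. The planned pair does not.

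**Step 4. Vary the assumption.** With rem per mCi 20% lower or higher (0.04992 or 0.07488):

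- Two [18F]FPEB scans: 2.000 to 2.998 rem
- Two of each tracer: 2.474 to 3.473 rem
- Three of each tracer: 60 × 0.04992 + 0.7164 = 3.712 rem, to 60 × 0.07488 + 0.7164 = 5.209 rem (0.7164 = 3 × 0.2360 + 6 × 0.0014)

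The pair would meet the 1.652 rem cap only if rem per mCi were at most (1.652 − 2 × 0.0014) / 40 = 0.0412, which is 34% below 0.0624.

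**Step 5. Room for prior exposure under 5 rem.** At the stated maximum, 5 − 1.652 = 3.348 rem. At 20 mCi with three of each tracer, 5 − 4.460 = 0.540 rem.

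**The case against.** The strongest reply is that the document already contains the controls. The 20 mCi figure is an upper bound, not a prescribed dose, so a 5 mCi injection satisfies every section at once. The acquisition text and the radiotracer section both give 5 mCi, the radiation section caps the subject's total at 1.652 rem, and nobody may be scanned before the radiation committee approves. On this view the rem scenarios need staff to ignore several other instructions. They also rest on an assumed scaling and an arbitrary range.

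Most of that is fair. A 20 mCi injection is unlikely in practice, and the rem figures only illustrate the size of the discrepancy. The 5 rem annual guideline belongs in the picture too: under proportional scaling even six injections come to 4.460 rem, below it for someone with no prior exposure, although a dose per mCi 20% higher would pass it. The 10 mCi figure is the total for two planned injections. It is not a separate rule, and a repeat scan would add to it.

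None of this reconciles a 20 mCi ceiling with a 7 mCi single-administration limit. That comparison needs no dosimetry assumption. The other controls make the error less likely to cause harm, but they leave it in the procedure text.

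**Conclusion.** The concern holds and must be fixed. The [18F]FPEB ceiling in PET Scans is wrong as written: it is 4 times the 5 mCi given in three other places and 2.86 times the single-administration limit that the protocol quotes. Those ratios rest only on figures in the document.

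The breach of the 1.652 rem cap by two scans at 20 mCi assumes proportional dose, but it survives a dose per mCi up to about one third lower. A single scan would not breach that cap.

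The 5 mCi figure is the one to keep, because the stated dosimetry is attached to it. The 20 was probably carried over from the matching [11C]ABP688 sentence, where it is correct. The documents do not say so, and the conclusion does not depend on it. No hypothesis, endpoint, sample size or analysis is affected.

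**What to change.** In Section 4.4, PET Scans, change the [18F]FPEB ceiling from 20 mCi to 5 mCi, so that it matches PET Data Acquisition and Analysis, Risks Associated with Radiation and Section II.A. Leave the 20 mCi for [11C]ABP688 as it is. The totals of 1.102 and 1.652 rem already rest on 5 mCi and need no change.

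The cost is one number in one sentence, made as a wording amendment.
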